The SBTR has been successfully employed as a primary outcome in our Goal 2 project ([name], Vujnovic et al., 2010; see preliminary study 2), along with two other IES-funded projects, one a between-group study of school-wide social and character development programs ([name], P.I., <http://www.sacdprojects.net>), and the other a study designed to investigate the best dose and sequencing of school-based treatments for children with ADHD ([name], P.I., R324B06045). The SBTR observation system has good inter-rater reliability – the mean difference between the observers on total rule violations recorded was 1.8 (SD=2.3; Range=0-12). For the total rule violations variable, the correlation between the two observers was .96 (p < .001), supporting the inter-rater reliability of the observation measure. The SBTR observation system also demonstrated moderate correlation with the DRC recorded by the teacher (r= -.46), suggesting the half-hour observation relates in the expected manner to the DRC completed over an entire school day ([name], Vujnovic, et al., 2009).

The SBTR observations will occur on three separate days in the month of January (before intervention begins) and three separate days in the month of May for each child. Each observation will last for thirty minutes. Time of day and activity will be controlled. Observers will be blind to the child's treatment condition. To ensure the reliability of this measure, 20% of observations will be completed simultaneously with a second observer to allow the calculation of estimates of reliability. Please see the Table in the Treatment Integrity section below for how these observations are independent and distinct from the integrity observations.

Teacher ratings of behavior. Teachers will be administered the following measures during the first two weeks of the month of January and again in May. The following measures will be used as indicators of student outcomes as secondary measures to the primary observational measure.

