Positive Student-Teacher Interactions. The ratio of positive to negative statements issued by the teacher on the SBTR observational measure will be used as an indicator of student-teacher interactions, with classrooms that have a positive environment having a larger number (i.e., more positives than negatives) relative to those that have a negative environment (i.e., fewer positives than negatives). Prior studies have demonstrated this information can be reliably collected (Vujnovic, et al., 2014). Further, these rates of positive to negative statements can be reliably modified based on background behavioral interventions such as the DRC ([name] et al., 2007). This measure will be collected across SAU and DRC groups.

Teacher Feedback for Targeted Behaviors. Observers in the DRC and SAU groups will have a list of the child's DRC/ITBC targets for each of their classroom observations. Observers will record the frequency of targeted behaviors exhibited as well as the number of targeted behaviors that receive appropriate feedback from the teacher. Observers will be blind to treatment condition. This approach to recording targeted behaviors and denoting which were responded to appropriately is part of the SBTR observation system developed by our group and used successfully in a number of school settings ([name] et al., 2010; [name] et al., 2007; Vujnovic, [name], et al., 2014). In this case we will modify the rule violations typically observed to be the individual child's targeted behaviors. The SBTR observation system has good inter-rater reliability: in one study the mean difference between the observers on total number of challenging behaviors was .53 (SD=3.3; Range=0-12). In an early childhood setting, agreement on the appropriate acknowledgement of challenging behavior was .68 ($p < .05$). For the total challenging behaviors variable, the correlation between the two observers was .94 ($p < .001$; [name] et al., 2010), supporting the inter-rater reliability of the observation measure. As a measure of validity, classroom challenging behaviors were negatively correlated with class climate $r = -.45$ (Massetti et al., 2007). The proportion of DRC/ITBC behaviors that were exhibited by the child that received feedback from the teacher will be used as an indicator of teacher monitoring and feedback of IEP goals.

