Fidelity of Teacher Implemented Interventions. Observers will collect information each month (January to May) on teacher responses to student behavior and general classroom management techniques. These observations will include a recording of frequency counts of social reinforcement (e.g., praise statements) as well as commands and negative feedback (i.e., reprimands) directed toward the individual student across the entire school day. These frequency counts will be combined into a ratio of positive to negative statements and used as an indicator of classroom environment. After each observation, observers will also complete a post-observation inventory form. These forms will ask the observer to rate the teacher's use of social reinforcement, commands, tone of voice, and the overall classroom climate on a 7-point Likert scale. An example of this rating to be completed after the observation is in Appendix C.

Integrity of DRC/Targeted Behavior Feedback. Once per month, observers blind to treatment group assignment will spend a full school day in the child's classroom. The observer will be provided a copy of the child's DRC/ITBC and will record a frequency count of the occurrence of each targeted behavior. In addition, targeted behaviors for which the child received specific feedback from the teacher (i.e., were acknowledged; recorded on the DRC/tracking mechanism if appropriate) will also be recorded. This will yield a daily rate of target behavior occurrence, as well as the proportion of targeted behaviors that received appropriate feedback. Observers will also record the latency between the occurrence of a targeted behavior and teacher feedback regarding the behavior using a stop-watch (a decision rule of latency greater than 1 minute will be used to document "no response" to a target behavior).

For children in the DRC group, we will be able to obtain a sample of the proportion of DRC targets appropriately monitored by the teacher with feedback provided. The observer's completed DRC tracking sheet will also be compared to the DRC completed by the teacher to ascertain a sample of the accuracy of the report sent home to the parent each afternoon. This comparison will be made by the investigators/project coordinator to maintain observer blinds.

Integrity of Home Rewards for School Performance. Following each of the all-day school observations (i.e., monthly), SAU/DRC families will be

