estimating equations for both the post-test score and mediators. Specifically, a path model will be estimated in which post-test scores are regressed on a dichotomous indicator of treatment, covariates described above (including pre-test scores and moderators), and on three mediators, measured as aggregate variables across the treatment period, including the quality of the classroom environment (ratio of positive to negative comments direct to the target child), consistency of teacher feedback in the classroom and home-based consequences related to school behavior. Moreover, the mediators will be simultaneously regressed on the indicator of treatment. A prototypic model is depicted below. The dashed line from covariates to post-test indicates that this actually refers to a block of variables that are omitted for presentation purposes A formal evaluation of mediation comes from

tests of whether the product of the coefficients relating treatment to mediators and mediators to outcomes (i.e., the indirect effects) differs from 0 (Bollen, 1987; MacKinnon, 2008). Whereas the joint test of the set of product terms (i.e., $a*d = b*e = c*f = 0$) provides an omnibus test of mediation, individual tests of products (i.e., $a*d = 0; b*e = 0; c*f = 0$) informs the contribution of each specific mediator. When combined with information regarding tests of indirect effects, the statistical significance

of the direct effect of treatment on post-test scores informs whether partial (i.e., if the path 't' is statistically significant) or complete (i.e., if the path 't' in the figure is not statistically significant) mediation is present. All tests of mediation will be based on the use of bootstrapped standard errors, which results in better statistical power and avoids having to make potentially unrealistic distributional assumptions about the mediated effect (MacKinnon et al., 2004; Preacher & Hayes, 2008). All mediated effects will be tested using Mplus software which includes facilities for testing individual and compound sets of mediated effects, as well as the use of bootstrapped standard errors (Muthén & Muthén, 2006).

17.2 If applicable, provide a power analysis.

NOTE: This may not apply to certain types of studies, including chart/records reviews, survey studies, or observational studies. This question is asked to elicit whether the investigator has an adequate sample size to achieve the study objectives and justify a conclusion.

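### Aim 3 does not fix the source or months of the classroom-environment mediator and, as written, admits May values taken alongside the outcome

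*Combined protocol and SAP*

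**What the plan says.** Four places in the protocol bear on this mediator.

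- **Section 10.2, Positive Student-Teacher Interactions** (the mediator definition): "The ratio of positive to negative statements issued by the teacher on the SBTR observational measure will be used as an indicator" of student-teacher interactions.
- **Section 10.2, Observations of Classroom behavior, and the schedule table at the end of 10.2**: SBTR sessions take place on "three separate days in the month of January (before intervention begins) and three separate days in the month of May". They last 30 minutes each and give the primary observational outcome. The section says they are separate from the integrity observations.
- **Section 10.2, Fidelity of Teacher Implemented Interventions**: "Observers will collect information each month (January to May) on teacher responses to student behavior". These are full-day visits with counts for the individual child, and "These frequency counts will be combined into a ratio of positive to negative statements and used as an indicator of classroom environment".
- **Section 17.1, Aim 3**: the three mediators are "measured as aggregate variables across the treatment period", and "the mediators will be simultaneously regressed on the indicator of treatment". The text names neither the source of the ratio nor the months in the aggregate. It lists pre-test scores and other covariates for the outcome equation. It mentions no January value of the mediator in either equation.

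**The concern.** Aim 3 asks whether better teacher-child interaction produces better classroom behaviour. The negative half of the ratio is made up largely of reprimands, and reprimands respond to misbehaviour. A child who breaks fewer rules in a session will tend to draw fewer reprimands in it. If ratio and outcome come from the same session, the outcome drives the mediator, and the path model will still report an indirect effect. Section 10.2 predicts that the three mediators together will fully account for the treatment effect, so an artefact in this direction would look like confirmation.

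Leaving the source and months open also allows a choice between two versions of the ratio after results are seen. Without the mediator's January level, stable differences between teachers stay in both paths.

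**Working it through.** **1. Counting sessions (10.2 schedule table)**

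| Source | Jan | Feb | Mar | Apr | May | Feb–Apr |
|---|---|---|---|---|---|---|
| Outcome SBTR | 3 | 0 | 0 | 0 | 3 | 0 of 6 |
| Full-day visit | 1 | 1 | 1 | 1 | 1 | 3 of 5 |

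If the ratio comes from the SBTR sessions, and pre-intervention January lies outside the treatment period, only the May outcome sessions remain. If it comes from the full-day visits, May still lies inside the treatment period, because 10.1 places the post-test in May after 16 to 20 weeks of treatment. Either way a May value can enter.

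**2. Inputs for a size estimate**

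From section 17.2: N = 216, d = .50, covariate R² = .45. With two-sided alpha .05 (assumed; the power text gives none), total N for Aim 1 is 2 × 2 × (1.96 + 0.84)² × .55 / .50² ≈ 69. The t-based version gives 71.04, against the stated 71, so the inputs are read as intended. The stated mediation power of over .80 cannot be reproduced because no path sizes are given.

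**3. Simulation with no true mediation**

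- Baseline behaviour B0 has variance 1. Behaviour at each later occasion is .67·B0 − .5·T + e, with var(e) = .55 (.67² ≈ .45). Residuals correlate ρ between occasions.
- The ratio only reacts: −.45 × concurrent behaviour + teacher trait + noise, with SD .6 for each of the last two. The slope borrows the size of the r = −.45 between challenging behaviour and class climate quoted in 10.2. Slope and SDs are assumptions.
- Mediation is declared when treatment to mediator, and mediator to outcome (given T and B0), both have p < .05. This stands in for the bootstrap test. There are 2,000 runs per cell (standard error at most about 1 point).

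| Mediator | ρ = 0 | ρ = .2 | ρ = .4 |
|---|---|---|---|
| May, same sessions as outcome | 39% | 42% | 41% |
| January + May SBTR mean | 14% | 17% | 16% |
| Five-month mean, May visit on a separate day | 2% | 9% | 26% |
| Five-month mean, May visit sharing the outcome behaviour | 13% | 28% | 37% |
| Feb–Apr, adjusted for January ratio | 4% | 30% | 72% |
| Feb–Apr, adjusted for January ratio and Feb–Apr behaviour | 5% | 4% | 4% |

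With both SDs at .3 or .9 instead of .6, the first row ranges from 21% to 77% and the last from 2% to 5%.

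**4. Reading the table**

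Moving the mediator to February to April is not enough. When behaviour is correlated across months, earlier behaviour drives the earlier ratio and also predicts May behaviour. Adjusting for February to April behaviour removes this. The last row assumes that behaviour is counted without error. With a daily reliability of .8 it becomes 4%, 5% and 9%; with .5 it becomes 4%, 12% and 34%.

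**The case against.** The best defence is that the full-day visits are the intended source. Section 17.1 describes comments to the target child, which matches the fidelity text. Outcome and integrity observations are declared distinct. Section 10.2 also uses SBTR as the name of a coding system, including for target-behaviour feedback, so naming it in the mediator definition need not mean the six outcome sessions. This is plausible, and it removes the same-session problem. It does not settle the source, because the section that defines the mediators says otherwise, and it leaves the May visit in the aggregate.

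A reader might infer that the trial cannot show that the mediator came before the improvement. The documents do not support that: three visits fall between the January set-up month and the May outcome. Nor is 40% the error rate of the planned analysis. It belongs to one reading, and the separate-day five-month mean gives 2% to 26%. A reader might also infer that a January + May mean halves the treatment effect on the mediator. No text proposes that mean, and the January SBTR sessions precede treatment.

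Two further points stand. The r = −.45 comes from another setting and is not a causal slope from child to teacher. The Aim 3 path diagram is not in the copy reviewed, so the missing baseline mediator is inferred from the prose alone.

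**Conclusion.** The point holds as a gap in the Aim 3 specification that should be closed before analysis. Two parts of 10.2 give different sources for one ratio, 17.1 chooses neither source nor months, and May values concurrent with the outcome are admitted on both readings. Following the mediator definition literally allows reverse causation to be reported as mediation.

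The direction of the artefact follows from how ratio and outcome are built. Its size does not: the simulated rates are illustrative and depend on an assumed slope, assumed variances and an assumed correlation across months. The same-session problem applies to the SBTR outcome. For outcomes rated by teachers in May the issue is concurrency only. Aim 3 is explanatory, and the Aim 1 comparison and the sample size are untouched.

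**What to change.** In 10.2 (Mediators) and 17.1 (Aim 3):

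1. State that the ratio comes from the February, March and April full-day visits, not from the outcome SBTR sessions and not from May. Build the other two mediators from the same months, with the family calls that follow those visits.
2. Adjust the ratio's mediator and outcome equations for the January SBTR ratio, which precedes intervention. For the other two mediators, do this only where a pre-randomisation value exists. That is doubtful for teacher feedback, because 10.1 has the target lists built with a consultant who is assigned after randomisation.
3. Put February to April target-behaviour frequency, already counted at those visits, in the outcome equation of the main Aim 3 model. Report the model without it alongside.

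No new data collection is needed. The mediator averages three days instead of five and is slightly less reliable. Step 3 makes the test conservative: any true mediation that works through behaviour already improved by April is adjusted away. It also protects only as well as behaviour is measured, so the reliability of those counts should be reported.

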IEP Quality. IEP quality will be assessed using a composite rating by study investigators. Prior to quality ratings, IEPs will be de-identified to remove the participant name and information as well as any information about the school or district. Ratings will evaluate the alignment between needs listed in the IEP with goals/objectives stated in the IEP. This will be one way to determine the quality of the IEP document itself – well-written IEPs should have IEPs with close alignment between academic, behavior, and social/emotional needs and the goals to realize improvement (see appendix C for an outline of the coding sheet to be used in the present study; Pariseau, 2011). We will also track which goals are added by consultants to the DRC that were noted as needs by the teacher, but not listed on the IEP. The occurrence of these issues may indicate that the IEP is outdated, poorly constructed, or not reflective of current behavior. These indicators will comprise an IEP quality score investigated as a moderator. Specifically, the score will be calculated as: (Alignment between needs and goals + additional targets added)/overall alignment). A score of 1 would indicate perfect alignment whereas a score below 1 would indicate discrepancy between needs and goals.

Mediators

Three key components of the DRC intervention that are central to our logic model (see figure in the introduction) will be investigated as mediators of treatment outcome. It is expected that relative to the SAU group, the children in the DRC condition will experience a more positive classroom environment, receive more consistent feedback from teachers, and experience more consistent home-based consequences for school behavior. These three variables will each have a partial mediating effect, and the sum total will fully mediate the effect on treatment outcome.

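### Aim 3 treats three aggregated mediators as error-free and gives no reliability for any aggregate, although path t, which decides full or partial mediation, is sensitive to mediator error.

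*Combined protocol and SAP*

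**What the plan says.** Section 10.2 (Mediators) names three mediators: the ratio of positive to negative teacher statements, teacher feedback on targeted behaviors, and home consequences for school behavior. It predicts the result: "These three variables will each have a partial mediating effect, and the sum total will fully mediate the effect on treatment outcome".

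The feedback mediator is defined there as follows: "The proportion of DRC/ITBC behaviors that were exhibited by the child that received feedback from the teacher will be used as an indicator". The supporting reliability text gives a mean observer difference on counts and two coefficients. One is for counts: "For the total challenging behaviors variable, the correlation between the two observers was .94". The other is for acknowledgement: "In an early childhood setting, agreement on the appropriate acknowledgement of challenging behavior was .68".

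The feedback data come from monthly visits: "Once per month, observers blind to treatment group assignment will spend a full school day". The home-reward calls follow those visits: "Following each of the all-day school observations (i.e., monthly), SAU/DRC families will be" called or texted the next morning.

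Section 17.1 (Aim 3) enters "three mediators, measured as aggregate variables across the treatment period" in a path model in Mplus with bootstrapped standard errors. Mediation is called partial if direct path t is significant and complete if it is not. Neither that section nor the power section (17.2) describes a latent variable, a reliability correction or a sensitivity analysis for measurement error.

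**The concern.** A regression on an observed score treats that score as exact. If the score carries random error, its path to the outcome is attenuated. What the mediator fails to carry then appears in the direct path. For mediators that all act in the same direction as the treatment effect, this works against the plan's own hypothesis: a correct logic model can look like partial mediation, and a real indirect effect can be missed.

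The plan gives no figure by which to judge how serious this is. The .94 describes the denominator of the feedback proportion. The .68 is the only figure on acknowledgement, but it comes from an early childhood setting, its index is not named, and it describes observer agreement rather than an average over several days. The other two mediators have no coefficient at all. The 20% double observation in Section 10.2 is stated for the SBTR outcome observations, not for the monthly visits.

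**Working it through.** **The plan's own figures.** Section 17.2 gives d = .50, covariate R² = .45, power .80 and N = 71 for Aim 1. The normal formula at two-sided .05 (alpha is assumed; it is not stated) gives 4 × (1.960 + 0.842)² × .55 / .50² = 69.1, or 70 in whole pairs. A t-based version gives 72. The stated 71 reproduces, so d = .50 and residual variance .55 are used below. The Aim 3 claim of power above .80 cannot be reproduced, because no path coefficients are given.

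**Reliability of the average.** The visits run from January to May: five days, or four if January is left out as set-up. Spearman–Brown, kρ/(1 + (k − 1)ρ), from ρ = .68:
- k = 4: 2.72/3.04 = .895
- k = 5: 3.40/3.72 = .914

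This holds only if independent observer error is the sole error. Observer agreement does not include day-to-day variation in the teacher. Suppose, as an assumption, that 50% of one-day true variance is stable over months. Single-day reliability is then .34, and the average reaches .67 (four days) or .72 (five). At 70% stable, it reaches .78 or .82. So .68 to .91 is a reasonable range, and the documents do not narrow it.

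**Leak into path t.** Assumptions: N = 216, 108 per arm; total effect .50, fully mediated; three mediators with equal shares, each raised .8 SD; within-arm reliability ρ; no mediator–outcome confounding. With Σ the within-arm mediator covariance and Θ = diag(1/ρ − 1), the estimated paths are (Σ + Θ)⁻¹Σb.
- Uncorrelated mediators: the direct share is the mean of (1 − ρ). Feedback alone at .68: .32/3 = 10.7%. All three at .68: 32%.
- Correlation .3, all at .68: 1.6/(1.6 + .4706) = .773, so the direct share is 22.7%.
- Correlation .3, feedback alone at .68: the feedback variance not shared with the other two is 1 − .18/1.3 = .8615. Its path is multiplied by .8615/(.8615 + .4706) = .647. Each of the other two is multiplied by 1 + .353 × .3/1.3 = 1.08. The direct share is 1 − (.647 + 2 × 1.0815)/3 = 6.3%.

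The rejection rates come from simulation with 6,000 trials per case. They use the ordinary t test at 5%, not the planned bootstrap.

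| Error in | Direct share, correlation 0 / .3 | t significant, correlation 0 / .3 |
|---|---|---|
| none | 0% / 0% | 5% / 5% |
| feedback only, .914 | 2.9% / 1.8% | 5% / 5% |
| feedback only, .68 | 10.7% / 6.3% | 8% / 6% |
| all three, .914 | 8.6% / 5.6% | 7% / 6% |
| all three, .80 | 20% / 13.5% | 15% / 11% |
| all three, .68 | 32% / 22.7% | 32% / 22% |

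**Direction.** The 1.08 above shows that attenuation is not universal. When mediators are correlated and differ in reliability, the better-measured paths are overstated, here by 8% (14% at correlation .5). Section 17.1 tests each product separately, so credit can shift between mediators.

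**Power for one indirect effect** (joint-significance approximation; standardized paths assumed equal). At .26, power is .95 without error, .92 at ρ = .914 and .79 at .68. At .20, it is .71, .66 and .47.

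**The case against.** A reader might infer that the feedback mediator has reliability .68, so that about a third of a fully mediated effect will be reported as direct. The documents do not support this. The 32% arises only when all three averages have reliability .68 and the mediators are uncorrelated. The .68 belongs to one mediator's acknowledgement judgement, in another setting, before averaging over days. With error in feedback alone at .91, t is significant at close to its nominal rate. Even with all three at .91 the plan would still declare complete mediation in about 93–94% of trials.

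A reader might also infer that the home-reward mediator rests on five calls and nothing else. Section 10.2 also has teachers ask the child the next morning and record the reward. In the DRC arm parents note rewards on the daily card, although that source has no SAU counterpart. Nor is the .68 concealed; it stands beside the .94.

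Finally, observed-variable mediation is conventional, and Aim 1 is untouched. A correction based on month-to-month agreement could over-correct, because DRC goals are adjusted monthly and real individual change would count as error.

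All of this stands. It limits the size of the problem and shapes the remedy. It does not supply the missing reliabilities, and it does not justify reading full mediation from a non-significant t.

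**Conclusion.** The point holds as a gap in the Aim 3 analysis, not as a demonstrated large bias. The mediators enter as error-free, no aggregate has a stated reliability, and the full-mediation hypothesis is decided by a path that mediator error usually pushes away from zero. The direct share runs from about 2% to 32% and the chance of a significant t from about 5% to 32%, depending on how many mediators carry error and how much. These figures rest on assumed mediator effects (.8 SD), equal shares, correlations of 0 to .3 and no mediator–outcome confounding. The documents give none of these. The usual direction is understated indirect effects, with the exception for better-measured correlated mediators. Aim 1 efficacy is unaffected.

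**What to change.** In Section 17.1 (Aim 3):
- Keep the planned observed-aggregate model and add a reliability-corrected model in the same Mplus set-up. Either use the monthly post-baseline visits or calls as indicators of a latent mediator, or use a single indicator with error variance estimated from the trial's own monthly data. In the second case, vary that error variance over a range, so that real change over months is not simply counted as error.
- Report the reliability of each aggregate, and the size and interval of the indirect and direct effects under both models.
- Do not label mediation complete or partial from the significance of t alone.

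In Section 10.2, state that .94 applies to behavior counts, and that .68 is an observer-agreement figure from another setting, not the reliability of the averaged mediator.

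Cost: analysis-plan wording and a larger model, with no new data, visits or staff. Intervals will be wider; in simulation, standard errors rose by up to about 20%. The model may be hard to estimate for home rewards, because most SAU contacts are expected to report none. For that reason the corrected model should accompany the planned one rather than replace it.

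### The Aim 3 climate mediator is a raw positive-to-negative ratio; neither it nor the feedback proportion has a rule for a zero denominator or for pooling counts

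*Combined protocol and SAP*

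**What the plan says.** Three places define the climate mediator, all as positives divided by negatives.

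- Section 10.2, Mediators, Positive Student-Teacher Interactions, takes it from the classroom observation code: "The ratio of positive to negative statements issued by the teacher on the SBTR observational measure will be used". Section 10.2 says of those SBTR sessions: "Each observation will last for thirty minutes". There are three in January, before the intervention, and three in May.
- Section 10.2, Fidelity of Teacher Implemented Interventions, takes it from the monthly visits, January to May. These count praise together with "commands and negative feedback (i.e., reprimands) directed toward the individual student across the entire school day". The text then says: "These frequency counts will be combined into a ratio of positive to negative statements and used as an indicator of classroom environment".
- Section 17.1, Aim 3, enters it in the path model as the "ratio of positive to negative comments direct to the target child".

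The feedback mediator (section 10.2, Teacher Feedback for Targeted Behaviors) is "The proportion of DRC/ITBC behaviors that were exhibited by the child that received feedback from the teacher". Its denominator is a count of the child's own targets: "In this case we will modify the rule violations typically observed to be the individual" child's targeted behaviours.

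Section 17.1 says that the three mediators are aggregated over the treatment period, without saying how. It also allows power transformations for non-normal outcomes and specifies bootstrapped standard errors for mediation tests. Section 17.2 relies on full information maximum likelihood (FIML) for Aim 3, so that all 216 children contribute, and claims power above .80 for moderate indirect effects. No section assigns a value when either denominator is zero, or says whether commands count as negative statements.

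**The concern.** A ratio of two counts is undefined when the lower count is zero and unstable when it is one or two. The logic model in section 10.2 expects a more positive classroom environment in the DRC arm. If that includes fewer reprimands, small denominators will be more common among DRC children and among those whose climate improved most. A few very large ratios then carry high leverage in both the treatment-to-mediator and the mediator-to-outcome regressions.

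The choice of aggregation matters as well. A mean of per-visit ratios is undefined if any one visit has no reprimand, unless such visits are dropped. A ratio of summed counts is undefined only if every visit has none. The plan permits either, and a choice made after seeing the data could decide the Aim 3 result.

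The feedback proportion raises a narrower problem. It lies between 0 and 1, so it cannot produce outliers, but it is 0/0 when no target behaviour is seen. Left to FIML, that child is treated as having a missing value, although the child was fully observed.

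**Working it through.** **The plan's own figure.** Section 17.2 gives power above .80 for Aim 3 at N = 216 but no path sizes, so it cannot be reproduced from its own inputs. A joint-significance simulation at N = 216, with both standardised paths assumed to be 0.20, 0.24 or 0.30 and two-sided alpha assumed to be 0.05, gives power of 0.71, 0.90 and 0.99. The claim is plausible for a well-behaved mediator.

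**Zero denominators.** The documents give no reprimand counts, so the mean m per observation is an assumption. For Poisson counts, P(zero in one observation) = exp(-m).

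- One 30-minute session at m = 1, 2, 3: exp(-1) = 0.37, exp(-2) = 0.14, exp(-3) = 0.05.
- At least one zero in three sessions, 1 - (1 - exp(-m))^3: 0.75 at m = 1 and 0.35 at m = 2.
- Four monthly full-day visits (February to May taken as the treatment period), at least one zero, 1 - (1 - exp(-m))^4: 0.84, 0.44 and 0.03 at m = 1, 2, 5 per day.
- The same four visits with counts summed first, exp(-4m) x 108: 2.0, 0.04 and about 0 undefined children per arm at m = 1, 2, 5.
- Summed counts with strong variation between children (negative binomial, k = 1), 108/(1 + 4m): 21.6, 12.0, 5.1 and 2.6 per arm at m = 1, 2, 5, 10.

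Pooling largely removes outright loss unless reprimands are very few or very unevenly spread across children.

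**Direction of bias.** Assume 6 positives per session and three sessions pooled (18 positives), with a mean of 1 negative per session in one group and 2 in the other, so N is Poisson with mean 3 or 6. Among children with a defined value the expected ratio is 18 x E[1/N | N > 0]:

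- mean 3: 18 x 0.4327 = 7.79, against a true 6.0;
- mean 6: 18 x 0.2078 = 3.74, against a true 3.0.

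The contrast is 7.79 - 3.74 = 4.05 against a true 3.0. Here the raw difference is exaggerated, not attenuated.

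**Effect on the test.** A simulation used 216 children, four visits, overdispersed counts, both standardised paths 0.3, and positive and negative rates log-linear in a latent climate score. Power of the joint-significance test was:

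| Mean negatives per day | Mean of daily ratios (child dropped if any day undefined) | Ratio of summed counts | log[(P+0.5)/(N+0.5)], summed | P/(P+N), summed |
|---|---|---|---|---|
| 1 | 0.02 | 0.42 | 0.76 | 0.73 |
| 2 | 0.09 | 0.45 | 0.86 | 0.86 |
| 5 | 0.37 | 0.46 | 0.91 | 0.90 |
| 10 | 0.49 | 0.59 | 0.94 | 0.94 |
| 20 | 0.47 | 0.62 | 0.93 | 0.93 |

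At 5 negatives per day, 36.5% of DRC and 26.6% of SAU children had at least one undefined day. With summed counts, fewer than 0.1% in either arm were undefined. The largest pooled ratio still lay about 6 to 8.5 standard deviations above the mean at every rate, with skewness of roughly 3 or more; skewness of the share and log forms was near zero.

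**Limits.** The simulation used complete cases and a normal-theory test, not FIML with the bootstrap, and no covariates. Its log-linear truth makes the raw ratio skewed by construction and favours the share and log forms. At 20 negatives per day zeros are negligible after pooling, so the gap of 0.62 against 0.93 there reflects scale and skew, not undefined values.

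**The case against.** The strongest reply is that this is a small specification gap. Only the monthly visits span the treatment period, they last a full school day, and pooling is a natural reading of an aggregate. On that reading undefined values nearly vanish, FIML keeps any remaining child, and bootstrapped standard errors avoid a normality assumption for the indirect effect. The mediators are dependent variables in the path model, so the transformation clause can be read as covering their skew. Only Aim 3 is involved; the Aim 1 efficacy test is untouched.

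Much of this stands. A reader might infer four stronger things that the documents do not support.

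- **That the best responders will lose their mediator values.** No reprimand rates are given, and pooled full-day counts make loss rare under most assumptions.
- **That the intervention aims at zero denominators.** Section 10.2 describes a positive classroom as one with more positives than negatives. Its example criteria are mostly non-zero, such as 8, 4 or 2 or fewer occurrences, and some targets are work-completion goals. Counting commands as negative would move the denominator further from zero.
- **That the treatment-to-mediator path is biased toward zero.** The calculation above shows the raw contrast exaggerated under one plausible set of rates.
- **That both mediators generate outliers.** The feedback proportion cannot. Its missingness depends on how many targets were exhibited, not on the proportion itself, and dependence on outcome, pretest and arm is compatible with FIML because all three are in the model.

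What the reply leaves open is that the data source is unresolved between a 30-minute session and a full day, that pooling is not stated, that no transformation defines x/0, and that bootstrapping does not remove the leverage of a few extreme ratios.

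**Conclusion.** The point holds as a weakness in how two Aim 3 mediators are defined. The climate mediator is a raw ratio that can be undefined and is likely to be strongly right-skewed, more so in children who receive few reprimands. The feedback mediator can be undefined or coarse, no more.

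The size depends on rates that the documents do not give. Zeros are plausible in single 30-minute sessions (37% to 5% at assumed means of 1 to 3) and rare once full-day counts are pooled. Under the assumed log-linear model the pooled raw ratio gave power of 0.42 to 0.62, against 0.73 to 0.94 for the zero-safe forms, so the stated power above .80 may not carry over to the mediator as defined. Part of that gap is the simulation's choice of scale. The direction of bias is not established, and Aim 1 is not affected.

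**What to change.** In sections 10.2 and 17.1:

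1. Name one data source for the climate mediator, reconciling the SBTR sessions with the monthly full-day visits, and list the visits that make up the treatment period.
2. Sum positive and negative counts over those visits before dividing.
3. Enter positive/(positive+negative) or log[(positive+0.5)/(negative+0.5)] in the path model, with the choice made before analysis. The log form is always defined; the share is undefined only if both sums are zero, and that case needs a stated rule.
4. State whether commands count as negative.
5. Compute feedback as behaviours with feedback summed over visits, divided by target behaviours summed over visits. State in advance how a child with no exhibited target behaviour at any visit is handled, for example with a separate indicator, instead of leaving that child to FIML by default.

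The same counts are collected, so the cost is wording. The downside is that the climate effect is read on a proportion or log scale, not as an x:1 ratio; the raw ratio can still be reported descriptively.
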